4.2 Study Endpoints

4.2.1 Active Treatment Period

4.2.1.1 Primary Endpoint for the ATP

The primary endpoint during the ATP will be the change from Baseline to the end of ATP (Week 20/Visit 8) in the acne-specific quality of life (acne-QOL) questionnaire score for those subjects who complete the 20-week ATP and are at least 75% adherent with the dosage regimen during study visits.

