Evaluation Criteria:	
The primary endpoint during the ATP will be the change from Baseline to the end of ATP (Week 20/Visit 8) in the acne-specific quality of life (acne-QOL) questionnaire score for those subjects who complete the 20-week ATP and are at least 75% compliant with the treatment regimen.
 
Secondary endpoints for the ATP will be:
 
 • The change from Baseline in the lesion count (nodules and inflammatory lesions) at the end of the ATP;

	
 • The change from Baseline in the acne-QOL score at Weeks 4, 8, 12, and 16 weeks; • The change from Baseline in the IGA at the end of the ATP in subjects who complete the 20-week ATP; • Treatment safety, as determined by the frequency and severity of adverse events (AEs) and local skin irritation. 
Primary endpoints for the PTP will be to determine:
 
 • The proportion of subjects who require retreatment with oral isotretinoin at any time during the PTP; and • The time at which retreatment is required. 
Secondary endpoints for the PTP will be to determine:
 
 • The proportion of subjects who require treatment with a prescription anti-acne medication other than oral isotretinoin at any time during the PTP; • The proportion of subjects who use an over-the-counter (OTC) anti-acne medication at any time during the PTP; • The severity of acne (lesion count and IGA) at the time of retreatment in subjects treated with a prescription or OTC anti-acne treatment; • The severity of acne (lesion count and IGA) at each visit; • The time to retreatment with a prescription or over-the-counter (OTC) anti-acne medication at any time during the PTP; • The acne-QOL at the end of the PTP; • Safety as assessed through the monitoring of AEs, laboratory test results, vital signs, and physical examinations.
Pharmacokinetics Evaluation Criteria:	Not applicable
Safety Evaluation Criteria:	During the ATP: adverse event (AE) incidence and severity, laboratory test results (hematology, serum biochemistry, lipid profile), pregnancy tests, vital signs (systolic and diastolic blood pressure, heart rate, respiratory rate) During the PTP: Serious AEs related to study drug.

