Statistical Methods:	Efficacy will be evaluated descriptively. Adverse events will be presented in data listings and summarized by frequency and severity. Laboratory and vital sign data will be presented in data listings. Abnormal laboratory findings will be presented. Results from the acne-QOL will be summarized.
Study Sites:	Approximately 20 study sites in the United States (US)
Planned Dates of Study:	January 2015 – April 2018

Table 1-1 Visit Schedule and Assessments – Active Treatment Phase (ATP)

	Visit 1	Visit 2	Visit 3	Visit 4	Visit 5	Visit 6	Visit 7	Visit 8 EOT
	Screening ≤30 days of Baseline ^a	Baseline	Week 2 ± 4 days	Week 4 ± 4 days	Week 8 ± 4 days	Week 12 ± 4 days	Week 16 ± 4 days	Week 20 ± 4 days
		0.5 mg/kg/day						1.0 mg/kg/day
Informed consent ^b including photographic consent	X							
Inclusion/exclusion criteria	X	X						
Demographics and medical history	X							
Physical examination	X							X
Vital signs and weight	X							X
Prior and concomitant medication assessment	X	X	X	X	X	X	X	
Childbearing potential (female subjects only) ^c	X	X						
Clinical laboratory assessment ^d	X	X	X	X	X	X	X	
Hematology								
Serum chemistry								
Pregnancy test ^e	X	X	X	X	X	X	X	X
Contraceptive counseling	X	X		X	X	X	X	X
Photography ^f		X		X	X	X	X	X
Quality of Life Questionnaire		X		X	X	X	X	X
Investigator's Global Assessment (IGA)		X		X	X	X	X	X
Lesion count ^g (nodules and inflammatory lesions)	X	X		X	X	X	X	X
Adverse event assessment		X	X	X	X	X	X	X
Issue 30-day supply of study medication		X	X	X	X	X	X	
Reconcile medication use and counsel as required			X	X	X	X	X	X

EOT = end of treatment

^a Females of childbearing potential must undergo a mandatory 30-day waiting period before receiving isotretinoin.^b Subjects under 18 years of age must sign and assent to participate in the study as well as have written informed consent from a parent or guardian. The parent or guardian must also give permission for a minor to receive contraceptive counseling.

- c. Childbearing potential includes dates of menstruation and forms of contraceptives currently used and to be used during the study.
- d. Laboratory assessments at Screening and EOT will include a complete blood count, fasting clinical chemistry, and fasting lipid profile. Laboratory assessments at all other visits will include only fasting clinical chemistry and fasting lipid profile.

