3.0 TRIAL OBJECTIVES AND PURPOSE

3.1 20-Week Active Treatment Period (ATP)

The primary objective during the 20-week ATP of the study will be to investigate the quality of life (QOL) of subjects who are taking Absorica® (isotretinoin) capsules twice daily (bid) without food for the treatment of severe recalcitrant nodular acne.

The secondary objective during the 20-week treatment period will be to investigate the efficacy and safety of Absorica® (isotretinoin) taken bid without food during the ATP.

Safety will be assessed through the monitoring of AEs, laboratory test results, vital signs, and physical examinations.

3.2 104-Week Post-Treatment Period (PTP)

The primary objective during the 104-week PTP of the study is to determine both the time to retreatment and the proportion of subjects who require retreatment with oral isotretinoin during a 2-year PTP.

The secondary objectives during the PTP are:

- To investigate the QOL at the end of the 2-year PTP;
- To investigate the severity of the acne over time, as measured by the Investigator's Global Assessment (IGA) and lesion counts;
- To document any acne treatment (prescription and/or over-the-counter [OTC]) used by those subjects;
- To evaluate the long-term safety during the 2-year PTP.

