4.0 STUDY DESIGN

4.1 Overall Study Design

This is a single-arm, open-label study consisting of 2 phases: a 20-week (5-month) open-label ATP and a 104-week (2-year) PTP. The total study duration is to be 124 weeks, excluding a screening period. During the ATP, after a Week 2 visit, visits will be scheduled at 4-week intervals for a total of 8 visits (1 screening visit, 1 baseline visit, and 6 on-study visits). During the PTP, the first visit will be 4 weeks after End of Treatment (EOT), the second visit will be 12 weeks after EOT, and subsequent visits will be scheduled at 26-week (\pm 2 weeks) intervals for a total of 6 visits.

Subjects will provide written informed consent, including mandatory photographic consent, on an informed consent form (ICF). Subjects who are under the age of 18 years will sign an assent form and their parent or guardian will sign the ICF. Subjects will then undergo a complete physical examination and will provide blood samples for hematology and fasting clinical chemistry, including liver function tests and a lipid profile with triglyceride levels. Female subjects of childbearing potential will be required to comply with mandatory pregnancy testing (see [Section 7.4.5](#)) and contraception specifications (see [Section 6.6](#)) before receiving study medication.

Subjects who meet the entry criteria will enter a 20-week ATP, during which they will receive Absorica® (isotretinoin) capsules. Dosing will be at an initial titration dose of approximately 0.5 mg/kg/day divided into 2 daily doses for the first 4 weeks, followed by 16 weeks of dosing with approximately 1 mg/kg/day divided into 2 daily doses. Study medication is to be taken

[figure not shown]
without food (ie, 1 hour before or at least 2 hours after the ingestion of food or beverages other than water).

Beginning at Visit 2 (Baseline) and continuing throughout the ATP and PTP (excluding Visits 3 and 9), subjects will be asked to complete an acne-specific quality of life (acne-QOL) questionnaire and photographs will be taken of the subject's face. Safety during the ATP will be assessed by adverse event (AE) monitoring and laboratory test results. Efficacy will be assessed by lesion counts (nodules, inflammatory lesions) and an IGA.

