5.0 SELECTION OF STUDY POPULATION

5.1 Subject Population

It is planned to enroll approximately 200 subjects at approximately 20 sites in the US in order to provide approximately 140 subjects who complete the ATP. An individual subject will be allowed to participate in the study one time only. A rationale for the choice of sample size is provided in [Section 8.2](#) of this protocol.

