8.3 Analysis Populations

Efficacy will be investigated in 2 populations. The PP population will be defined as including all randomized subjects who are at least 75% compliant with their assigned treatment, have no major study protocol violations, have a Week 20 count of total nodular lesions, and do not use any disallowed medications during the 20 weeks of treatment. The ITT population will be defined as including all subjects who are randomized and receive study medication.

The safety population will comprise all subjects who have consumed at least 1 dose of study medication, including those for whom dosing information is unknown.

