8.6 Quality of Life Analysis

The primary endpoint during the ATP will be the change from Baseline to the end of the ATP (Week 20/Visit 8) in the acne-specific quality of life questionnaire (acne-QOL) in those subjects who complete the 20-week ATP and are at least 75% compliant with the dosage regimen.

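### The primary acne-QOL result covers only 20-week completers with at least 75% adherence, and the supplied text commits to no Week 20 estimate in all dosed subjects beside it

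*Combined protocol and SAP*

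**What the plan says.** The ATP primary endpoint is the change in acne-QOL from Baseline to Week 20. Its population is given in three places of the combined protocol and SAP:

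- Section 4.2.1.1: "for those subjects who complete the 20-week ATP and are at least 75% adherent with the dosage regimen during study visits"
- Synopsis, Evaluation Criteria: "for those subjects who complete the 20-week ATP and are at least 75% compliant with the treatment regimen"
- Section 8.6: "those subjects who complete the 20-week ATP and are at least 75% compliant with the dosage regimen"

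Section 3.1 states the matching objective as "to investigate the quality of life (QOL) of subjects who are taking" the study drug without food. Section 5.1 plans to enrol about 200 subjects "in order to provide approximately 140 subjects who complete the ATP".

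Section 8.3 defines PP and ITT sets after the opening statement "Efficacy will be investigated in 2 populations". Section 4.1 says what efficacy means: "Efficacy will be assessed by lesion counts (nodules, inflammatory lesions) and an IGA". Section 8.4 covers the same two measures. Acne-QOL has its own Section 8.6, which names only the restricted set. The synopsis adds "Results from the acne-QOL will be summarized", without naming a population or visit.

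Section 8.2 plans 95% two-sided confidence intervals and no tests. Section 8.1 describes Section 8 as a summary of a SAP still to come.

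**The concern.** Completing 20 weeks and reaching 75% adherence are both known only after treatment starts, and both may be related to how a subject feels about the treatment. In a single-arm study no control group is selected in the same way, so the mean change in the chosen subjects is the whole finding. The planned interval reflects sampling error within those subjects and says nothing about how they were chosen.

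A reader who wants to know what subjects who start the course gain on average would not find it in the stated analyses. The data to answer that are largely planned already. Completers below 75% are scheduled for a Week 20 questionnaire. Drop-outs have scores from the visits they attended, and Section 7.2.8 asks for the questionnaire at early termination, although Section 5.4 qualifies this to where it is possible. No stated analysis of the primary measure uses these scores, and no missing-data assumption is given.

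**Working it through.** **1. Is an all-dosed Week 20 acne-QOL estimate stated anywhere?**

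| Place | What it covers |
|---|---|
| Synopsis, 4.2.1.1, 8.6 | Week 20 acne-QOL, completers with at least 75% adherence only |
| 4.2.1.2 | acne-QOL at Weeks 4, 8, 12 and 16; not Week 20 |
| 4.2.2.2 | acne-QOL at the end of the post-treatment period |
| 8.3 | ITT and PP sets, introduced for efficacy |
| 4.1, 8.4 | efficacy is lesion counts and IGA |
| Synopsis, Statistical Methods | acne-QOL to be summarized; no population or visit |

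None of these commits to the estimate. The ITT set in 8.3 would be the natural home for it, but it requires subjects to be randomized, and Section 6.4.1 says there is no randomization.

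**2. How many subjects are planned outside the set?**

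Inputs from Section 5.1: 200 enrolled, 140 completers. Planned share outside = 1 − 140/200 = 0.30, or 60 subjects, before the adherence filter. In reverse, 140/(1 − 0.30) = 200. That is only a consistency check, because the 30% comes from the same two figures; the documents give no SD, target precision or dropout rate from which 200 could be rebuilt. If 95%, 90% or 80% of completers reach 75% adherence (assumed), the set falls to 133, 126 or 112.

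**3. How far could the restricted mean differ from the all-subject mean?**

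Let s be the share kept and f the mean gain of excluded subjects as a fraction of the gain of those kept. The all-subject mean is s + (1 − s)f times the restricted mean, so

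excess = 1/(s + (1 − s)f) − 1.

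The documents give no value for f, so a range is shown.

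| f (assumed) | s = 140/200 = 0.70 | s = 140/190 = 0.737 (10 never dosed, assumed) |
|---|---|---|
| 1.1 | 1/1.03 − 1 = −3% | −3% |
| 1 | 0% | 0% |
| 0.5 | 1/0.85 − 1 = 18% | 15% |
| 0 | 1/0.70 − 1 = 43% | 36% |

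**4. How does this compare with the planned precision?**

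The 95% half-width at n = 140 is t(0.975, 139)/√140 = 0.167 SD of the change score. The selection shift is 0.30 times the gap in mean gain between kept and excluded subjects. It exceeds the half-width once that gap is larger than 0.167/0.30 = 0.56 SD.

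**5. What does setting drop-outs to zero change do?**

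With s = 0.70 it returns 0.70 of the completer mean. If drop-outs would in fact have gained as much as completers, that is 30% too low. If they fell below baseline, for example f = −0.25, the all-subject mean is 0.70 + 0.30 × (−0.25) = 0.625 of the completer mean, which is lower still. The zero-change analysis is therefore conservative in most settings but not a strict bound.

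**6. Is the 75% defined?**

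The synopsis refers to the treatment regimen and Section 8.6 to the dosage regimen; Section 4.2.1.1 alone adds a reference to study visits. Section 6.9 mentions a share of required doses, but to say who is counselled or may be withdrawn. What is counted for the endpoint, and over which window, is not stated.

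**The case against.** The strongest reply is that the set matches its objective. Section 3.1 asks about subjects taking the drug, the study is descriptive, and an on-treatment set is a legitimate choice. This stands, and it is why the restricted result should stay. A reader might infer that the primary endpoint itself is wrong; the documents do not support that.

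Secondly, Section 8 is a summary, and secondary populations and missing-data rules are normal SAP content. This also stands in part: the claim can only be that the supplied text states no such estimate, not that none will be made. However, where the supplied text does name a population for acne-QOL, it names only the restricted one.

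Thirdly, the ITT set might be said to cover acne-QOL as an efficacy measure. Sections 4.1 and 8.4 do not list it as one.

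Two stronger readings should be resisted. A reader might take 30% as the least that will be excluded. Section 5.1 gives a planning target, and if more subjects complete, fewer are excluded for non-completion. A reader might also conclude that the restricted mean must be too high. That is plausible, but nothing in the documents fixes the size or the sign.

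**Conclusion.** The concern holds as a gap in reporting. As written, the headline acne-QOL result is selected on two post-baseline events, and the supplied text commits to no all-dosed Week 20 figure beside it. On the planning figures about 30% of enrolled subjects lie outside the set before the adherence filter. The difference between the two means runs from none to 43% of the all-subject mean as the excluded subjects' gain goes from equal to nil, with 18% at half; a small difference the other way is possible. These sizes rest on the assumed relative gain and on 70% being retained.

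No type I error or power is at stake, since no test is planned. The issue is whom the estimate describes. It should be fixed, and the unseen SAP keeps confidence at medium.

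**What to change.** Keep the completer/75% result. Then, in the synopsis, Section 4.2.1.1 and Section 8.6:

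- Add the Week 20 change in acne-QOL with a 95% CI, without a test, in all dosed subjects with a baseline score.
- Use the observed Week 20 scores of completers below 75%.
- For drop-outs, use all scheduled scores and the early-termination score, assigned to the nearest scheduled visit, in a repeated-measures model assuming data missing at random. State that this largely estimates the outcome had they continued.
- Add one sensitivity analysis that sets drop-outs' change to zero, described as conservative and not as a strict bound.
- Report how many subjects are outside the primary set for non-completion and how many for adherence below 75%.
- Define the 75% for the endpoint (what is counted, over which window) in the same words in all three places.

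In Section 8.3, replace randomized with enrolled and state that the all-dosed set also applies to acne-QOL.

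This needs no new visits, subjects or assessments. The cost is wording, a little more analysis work, and a companion figure that may be smaller than the completer figure: 0.30 × 0.5 = 15% smaller if excluded subjects gain half as much.

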4.2.1.2 Secondary Endpoints for the ATP

Secondary endpoints will be:

- The change from Baseline in the lesion count (nodules and inflammatory lesions) at the end of the ATP;
- The change from Baseline in the acne-QOL score at Weeks 4, 8, 12, and 16 weeks;
- The change from Baseline in the IGA at the end of the ATP in subjects who complete the 20-week ATP;
- Treatment safety, as determined by the frequency and severity of AEs and local skin irritation.

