7.2.8 Early Termination

If a subject withdraws from the study during the ATP and prior to Week 20/Visit 8, the subject is to return to the site. All EOT procedures should be performed, including the administration of

the acne-QOL questionnaire, the lesion count, the IGA, and a pregnancy test (if applicable). The photography should be performed using the method assigned to the site.

If a subject withdraws from the study during the PTP and prior to Visit 14, the subject is to return to the site for an early termination visit. All EOS procedures should be performed, including the acne QOL, lesion count, the IGA, and photography. Subjects who require an additional course of isotretinoin therapy are to be discontinued after the EOS procedures are performed.

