8.2 Sample Size and Power Considerations

The sample size of 200 subjects was selected to provide adequate estimates of probable events in the population. Estimates of the endpoints of interest will be calculated with 95% 2-sided confidence intervals wherever possible. No statistical hypothesis tests are planned.

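### The end-of-treatment IGA endpoint is limited to 20-week completers; its lesion-count partner is not, and Section 8.3 calls for an ITT efficacy analysis that the IGA wording cannot supply

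*Combined protocol and SAP*

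**What the plan says.** Section 4.2.1.2 lists two efficacy endpoints for the ATP, and the synopsis repeats both:

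- Lesion count: "The change from Baseline in the lesion count (nodules and inflammatory lesions) at the end of the ATP". No subject set is given.
- IGA: "The change from Baseline in the IGA at the end of the ATP in subjects who complete the 20-week ATP".

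Section 8.3 states: "Efficacy will be investigated in 2 populations". The ITT set is everyone randomized who receives drug. Since Section 6.4.1 rules out randomization, I read this as all dosed subjects. The PP set requires at least 75% compliance, no major violation, no disallowed medication and a nodule count at Week 20. Section 8.4 promises descriptive statistics for lesion count and IGA alike. It assigns no population to either and gives no rule for missing or early values.

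For a subject who withdraws during the ATP, Section 7.2.8 says "All EOT procedures should be performed" and names both the lesion count and the IGA. Section 5.4 asks for the final evaluations where they can be obtained. Section 5.1 enrolls about 200 subjects to "provide approximately 140 subjects who complete the ATP".

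**The concern.** Section 4.1 says that efficacy is assessed by lesion counts and IGA, so these two endpoints carry the efficacy half of the secondary ATP objective. They should describe the same subjects, and as worded they need not.

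Completing 20 weeks is itself a post-baseline outcome. Section 5.4 allows treatment to be stopped for intolerance or significant disease, and subjects to be withdrawn for medical reasons or non-adherence. Section 6.9 allows withdrawal of subjects who take fewer than 75% of doses. Leavers are not replaced. A mean over completers therefore describes those who tolerated and continued treatment. With one arm, no between-group comparison can offset that selection.

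Section 8.2 says "No statistical hypothesis tests are planned". That does not lessen the concern: estimates with 95% confidence intervals are what the trial will deliver, so which subjects are averaged determines what the estimate means.

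**Working it through.** **1. Planned number outside the IGA result.** The inputs are about 200 enrolled and about 140 completers (Section 5.1).

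- Non-completers: 200 − 140 = 60, and 60/200 = 30%.
- The plan states no dropout rate. Section 8.2 says only "The sample size of 200 subjects was selected to provide adequate estimates of probable events in the population". Checking 140/(1 − 0.30) = 200 is circular, because the 30% comes from the same two figures.
- The 200 are enrolled, not dosed. If 10 or 20 never took drug (assumed), the share of dosed subjects left out is 50/190 = 26.3% or 40/180 = 22.2%. Hence up to about 30%.

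**2. The IGA wording against Section 8.3.**

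| Set | Contains early leavers? | Compatible with the IGA wording? |
|---|---|---|
| ITT (all dosed) | Yes | No: the endpoint exists only for completers |
| PP | Only those with a Week 20 nodule count | Yes, but the completer clause then adds little |
| 20-week completers | No | Yes, but Section 8.3 does not define this set |

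The IGA endpoint thus rests on a set that is neither of the two efficacy populations. The primary acne-QOL endpoint in Section 4.2.1.1 also names completers. The plan therefore writes this restriction down where it wants it, and its absence from the lesion-count bullet cannot be read as implied.

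**3. Are early-termination values end-of-ATP values?** Section 4.2.1.1, the synopsis and Section 8.6 equate the end of the ATP with Week 20/Visit 8 for acne-QOL. Table 1-1 places Visit 8/EOT at Week 20 ± 4 days. Section 7.2.8 applies the EOT procedures to a withdrawal before that visit but does not rename the visit. There are two readings:

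- Week 20/Visit 8 applies throughout. Early leavers then have no end-of-ATP value for lesion count or for IGA.
- The early-termination assessment stands in. No text says so.

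**4. How far the unstated rule could matter.** This is illustrative. Let r be the assumed fraction of the 60 who contribute an early count, and d the assumed difference in mean change between completers and leavers, in SD units. The leavers' share of the result is 60r/(140 + 60r). The pooled mean differs from the completer mean by d times that share.

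| r | Share | Shift at d = 0.5 SD | Shift at d = 1 SD |
|---|---|---|---|
| 0 (observed Week 20 only) | 0/140 = 0% | 0 | 0 |
| 0.5 | 30/170 = 17.6% | 0.088 SD | 0.176 SD |
| 1 | 60/200 = 30% | 0.150 SD | 0.300 SD |

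For scale, the 95% half-width of a mean is 1.96/√140 = 0.166 SD, or 1.96/√200 = 0.139 SD. The shift can be nil or larger than the confidence interval would suggest, depending on inputs that the documents do not give. The table pools leaving-visit values with Week 20 values, so it does not measure the effect of the fix below.

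**The case against.** The strongest reply has four parts.

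- **The restriction is disclosed.** It stands in the endpoint's own wording, for a secondary endpoint of an uncontrolled Phase 4 study whose primary ATP objective is quality of life. This stands as to importance. It does not remove the conflict with the ITT analysis.
- **Detail is deferred.** Section 8.1 calls Section 8 a summary of a fuller SAP, whose text is not in the supplied document. Visit mapping and missing-data rules usually belong there. This stands for the early-termination rule, which can be called absent only from the protocol. It does not cover the completer clause, which is protocol text. The SAP is due only before database lock, and in an open-label study results can be seen before then, so the rule is better fixed early.
- **End of the ATP already means Week 20.** This is the better reading. A reader might infer that leavers are dropped from the IGA result yet enter the lesion-count result at whatever week they left. The documents do not support that, because no text makes an early count the end-of-ATP value.
- **Section 8.3 does not rest efficacy on all dosed subjects alone.** Correct: PP is an efficacy population too, and it ties the nodule count to Week 20. The conflict is with ITT only.

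**Conclusion.** The point holds as an inconsistency with consequences. The IGA endpoint is limited to completers, the lesion-count endpoint is not, and the ITT efficacy analysis of Section 8.3 cannot be produced for IGA as worded. The completer-only result leaves out up to about 60 of 200 planned subjects (30%) on a post-baseline criterion. This rests on the planning figures in Section 5.1 and on reading ITT as all dosed.

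The protocol leaves open how early-termination assessments are used. On the Week 20/Visit 8 reading, early leavers lack an end value for both endpoints. The lesion-count result is then also confined to those with Week 20 data unless a method for missing values is stated.

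A reader might go further and put a figure on the resulting bias, or assume that the IGA result is flattered. The documents give no response, variability or withdrawal-reason data, so neither size nor direction can be derived. Leavers with poor response or intolerance would make completers look better, but nothing shows that this describes most of the 60. The plan should be changed on this point, although the endpoints are secondary and no test depends on them.

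**What to change.** In Section 4.2.1.2, the synopsis and Section 8.4:

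- Define both endpoints as change from Baseline at Week 20 in all dosed subjects (ITT), and delete the completer clause from the IGA bullet.
- Keep early-termination lesion counts and IGA at the week they were made, and do not treat them as Week 20.
- Estimate the Week 20 value, with a 95% confidence interval, by a method that uses all scheduled assessments (Weeks 4, 8, 12, 16 and 20) and suits the outcome. A repeated-measures model is one option. The choice should allow for the IGA being an ordered 0 to 5 grade and for nodule counts that may fall to zero. State the assumption made about missing values.
- Report completers and PP as supportive for both endpoints.

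The cost is wording and somewhat more analysis on data already scheduled for collection, with no added visits. The headline IGA figure may be less favourable than the completer-only one.
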